9.2 Laboratory Evaluations

9.2.1 Clinical Laboratory Evaluations

Laboratory tests to be performed at each visit are summarized in Appendix A (including approximate phlebotomy volumes) and listed by visit in Section 8.

9.2.1.1.1. Special Assays or Procedures

A summary of immunologic assays to be performed on blood specimens is shown in Table 9-1.

Table 9-1 Summary of Immunology Laboratory Evaluations

		Immunology	Approximate Blood Volume		Name and Location of Analysis
Sample Type	Assay	Endpoint	(per Visit)	Study Days	Laboratory
Whole blood	•	Primary	2 to 4 mL ^b	28, 56, 182, 365	SATVI, South Africa
QFT Gold Plus	responses QFT conversion by MTBVAC	Secondary, ^c	4 mL	56, 182, 365	SATVI, South Africa
Supernatants from whole blood ICS assay	ELISA/ Multiplex bead array for analysis of innate response cytokines	Future Exploratory	Not applicable	28, 56, 182, 365	SATVI, South Africa

- a. Stimulation conditions for days 28, 56, 182 and 365 include MTBVAC, CFP-10, ESAT-6, EspC and a "megapool" of peptides containing immunodominant *M. tuberculosis* epitopes, Nil and PHA. The higher blood volume at days 182 and 365 allows for an additional stimulation condition of a modified version of the "megapool" but containing only those epitopes shared by both BCG and MTBVAC to be added.
- b. Depending on age of infant as explained in footnote to Schedule of Events (Appendix A)
- c. If QFT positive at D56, D182 and D365 QFT samples will be stored for later analysis

9.2.2 Specimen Preparation, Handling, and Shipping

9.2.2.1 Instructions for Specimen Preparation, Handling, and Storage

Staff at the clinical trial site will refer to the most current version of the Laboratory Manual (provided under separate cover) for further instructions and additional information on specimen collection and processing.

9.2.2.2 Specimen Shipment

Staff at the clinical trial site will refer to the most current version of the Laboratory Manual (provided under separate cover) for further instructions and additional information on specimen shipping.

10 ASSESSMENT OF SAFETY

Responsibilities for Ensuring the Safety of Trial Participants

The national regulatory authority, the study sponsor (Biofabri), the institution through which the research is performed, and all members of the principal investigator's clinical team, share responsibility for ensuring that participants in this trial are exposed to the least possible risk of adverse events that may result from participation in this protocol.

Principal Investigator

The principal investigator has a personal responsibility to closely monitor trial participants and an inherent authority to take whatever measures necessary to ensure their safety. The principal investigator has the authority to terminate, suspend or require changes to a clinical trial for safety concerns and may delay a participant's investigational product administration or pause investigational product administration in the whole trial if the investigator has some suspicion that the investigational product might place a participant at significant risk. The principal investigator determines severity and causality with respect to the investigational product for each adverse event.

Responsibilities of the principal investigator may be assigned to a designee who is a medically qualified team member (who must be a sub-investigator in the case of assessment of adverse events); however, the accountability for the specific task remains with the principal investigator.

Study Sponsor

The sponsor (Biofabri) also has an institutional responsibility to ensure participant safety. This responsibility is vested in the local medical monitor and a DSMB (see Section 10.7).

Local Medical Monitor

The local medical monitor is a credentialed physician or surgeon in their country of residence with the necessary expertise to act in such capacity. The local medical monitor reviews the safety of the product for protocols in a specific region and, in conjunction with the sponsor, determines expectedness of related serious adverse events. The local medical monitor, in consultation with the sponsor, may assess the causality for adverse events and may upgrade or downgrade the causality determined by the principal investigator. The local medical monitor, like the principal investigator, is blinded.

Institutional Review Boards and Ethics Committees

The IRB/IEC has institutional responsibility for the rights, safety, and welfare of participants in clinical trials. The IRB/IEC has the authority to terminate, suspend or require changes to a clinical trial.

National Regulatory Authority

Since the national regulatory authority receives all expedited safety reports, it also has the authority to terminate, suspend or require changes to a clinical trial.

10.1 Specification of Safety Parameters

Safety parameters that constitute the primary outcome measures of the study are described in Section 4.2.1. The time periods for collection of adverse events are as follows.

Unsolicited Adverse Events

Unsolicited adverse events will be collected from informed consent until trial completion.

Solicited Adverse Events

Solicited systemic adverse events will be collected post-vaccination through the Study Day 28 visit (with diary cards to be used for 7 days after vaccination).

Solicited injection site reactions will be collected post-vaccination through the Study Day 56 visit (with diary cards to be used for 28 days after vaccination).

Solicited adverse events are events the participant is specifically asked about. These adverse events are commonly observed soon after receipt of vaccines. For this study, solicited adverse events to be collected include:

- Solicited systemic adverse events:
 - fever, irritability, vomiting, diarrhea, drowsiness, poor feeding, skin rash.
- Solicited injection site reaction adverse events:
 - pain, redness, swelling, ulceration, drainage, and regional lymphadenopathy.

Solicited adverse events of injection site reactions will be considered causally related to investigational product.

All participants' caregivers will be provided a diary card to record axillary temperature and information regarding occurrences of these specific events for the first 7 days (for systemic adverse events) or 28 days (for injection site reaction adverse events) of the solicited adverse event reporting period.

Serious Adverse Events

Serious adverse events will be collected throughout the entire study period (i.e., 365 days post-vaccination).

Site of Injection Examination

Site of injection examinations will be performed at the visits noted in the schedule of events in Appendix A. The following will be assessed at each examination:

• Tenderness/pain, redness, swelling, warmth, ulceration, presence of infection/abscess, crusting, drainage, scarring, and regional lymphadenopathy.

Any of the above-mentioned injection site reactions that meet adverse event criteria according to the Toxicity Table in Appendix C will be recorded as adverse events.

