- Record any adverse events, including unsolicited adverse events, solicited and unsolicited injection site reactions, and serious adverse events (including concomitant medications).
- 8. Examine site of injection (includes measurement of redness, swelling, and ulceration) and take a pus swab if discharge present.
- 9. Blood collection for:
 - Immunogenicity WB-ICS
 - QuantiFERON®-TB Gold Plus test

Study Day 120 ±7 days and Study Day 270 ±7 days

Home / telephonic visit if infant tested QFT positive at D56 to enquire about TB signs and symptoms and general well-being

Study Day 182

Allowable window for clinic visit is 182 ±14 days from Study Day 0 visit date.

- 1. Verbally reconfirm consent.
- 2. Update medical history including use of medications.
- 3. Screening for potential new TB exposure and TB symptoms.
- 4. Record feeding practice.
- 5. Vital signs (heart rate, respiratory rate, axillary temperature, weight and recumbent length).
- 6. Focused physical examination.
- 7. Record any adverse events, including unsolicited adverse events and serious adverse events (including concomitant medications).
- 8. Examine site of injection (includes measurement of redness, swelling, and ulceration) and take a pus swab if discharge present.
- 9. Blood collection for:
 - Immunogenicity WB-ICS
 - QuantiFERON®-TB Gold Plus

Partial Cohort Unblinding of Data Post Study Day 182

Once the last Cohort 3 Study D182 visit has been completed, an independent biostatistician be unblinded to available study data. At this point Cohort 1 and Cohort 2 participants will have completed all study visits and these participants and clinical team will be unblinded post Study D365 visit. All available safety data for all cohorts up to the last Cohort 3 Study D182 visit completion; and immunogenicity data for all cohorts up to each cohort's Study D182 visit, will be analysed by the independent, unblinded biostatistician and provided to DSMB for review to determine MTBVAC dose selection for the Phase III study. The Sponsor will review blinded data only in order to keep the blind until post Study D365 visit. The DSMB will be provided with the same blinded data along with unblinding vaccine recipient lists. The DSMB review will allow for a blinded recommendation and input into the dose selection for the Phase III study. For all cohorts, unblinding of the clinical team and participants will take place post Study D365 visit.

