12.4.4 Safety Analyses

12.4.4.1 Adverse Events

The primary endpoint is the frequency of adverse events (AEs) by MTBVAC dose compared to BCG. In order to assess the primary endpoint, analysis of the data will be preceded by a

blinded data review meeting in order to address population determination and miscellaneous data queries pertinent to analysis of the primary endpoint.

Safety and reactogenicity data will be evaluated by study arm and cohort in all participants in the safety analysis set. The primary variable for evaluation of safety will be the frequency of unsolicited, solicited adverse events and injection site reactions at all available post-vaccination time points. The number and percentage of participants with adverse events will be summarized by MedDRA system organ class (SOC) and preferred term (PT), as well as by severity and relationship to study vaccine. Informal between-group comparisons will be performed using the Chi-square or Fisher Exact test. The Cochran-Mantel-Haenzel test will be used to compare the effect of dose on reactogenicity (injection site adverse events).

Separate listings will be provided for participants with serious adverse events. SAEs may also be summarized by MedDRA system organ class and preferred term.

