APPENDIX A. SCHEDULE OF EVENTS

		Study day Visit Window (hrs/days)							
Evaluation	Screen	D0	D7	D28	D56	D182	D365	Post D365	Early termination
	NA	+96 hrs	±3d	±3d	±7d	±14d	±14d	NA	NA
Informed consent process	Ma								
Medical history	М								
TB symptoms or household TB contact	М	х	Х	х	х	х	х	х	х
Maternal HIV result available	М								
Verbally reconfirm consent	М	М	М	М	М	M	М	М	
Verify eligibility criteria	Х	Х							
Vital signs, length, weight		Х	Х	х	х	х	Х	Х	X
Record feeding practice		Х	Х	Х	Х	х	х	х	х
Physical examination		Х	Х	Х	Х	х	х	х	х
Recording of concomitant medication		Х	Х	х	Х	х	х	х	х
Randomization		Х							
MTBVAC/BCG administration		Х							
Safety blood sampling (mL) ^b			2						
QuantiFERON®-TB Gold Plus (mL)b					4 ^d	4	4		4
Whole blood (mL) ^b				2	2	4	4		
(12-hour WB-ICS)							7		
Distribute/review diary cards		Х	Х						
Solicited systemic adverse events (incl. concomitant medications)		х	x	х					
Unsolicited adverse events (incl. concomitant medications)		х	x	х	х	х	х		х
Solicited and unsolicited injection site reaction adverse events (incl. concomitant medications)		х	х	х	х				
Serious adverse events (incl. concomitant medications)		х	х	х	х	х	x		x
Site of injection examination swab if discharge		х	Х	х	х	х	х		x
Rescue dose BCG post unblinding of cohort ^c								x	
Approximate per visit phlebotomy volume (mL) ^a			2	2	6	8	8		4
Cumulative phlebotomy volume (mL)b			2	4	10	18	26		NA

^a Maternal - the mother signs once, antenatally, and thereafter reconfirms consent orally at each visit

^b Acceptable infant blood sample volumes in clinical research are limited to <3% of the total blood volume (TBV), and no more than 3mL/kg over an 8 week period

^c Telephonic contact/ home visit approximately 14 days post BCG to confirm infant's wellbeing incl. BCG injection site reaction

^d If QFT positive at D56 a home/telephonic visit will be done at D120±7d and 270±7d to monitor infant's wellbeing, specifically enquiring about TB signs and symptoms

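### Appendix A stops injection-site-reaction adverse events at D56, while Sections 10.1 and 12.4.4.1 carry them to the end of follow-up, and Section 10.1 cites the wrong grading table

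*Combined protocol and SAP*

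**What the plan says.** Section 10.1 sets three rules that bear on local reactions.

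- Solicited period: "Solicited injection site reactions will be collected post-vaccination through the Study Day 56 visit". The six solicited terms are "pain, redness, swelling, ulceration, drainage, and regional lymphadenopathy". Events in this category are taken as vaccine-related by default.
- Unsolicited period: "Unsolicited adverse events will be collected from informed consent until trial completion".
- Site examination, at the visits marked in Appendix A: "injection site reactions that meet adverse event criteria according to the Toxicity Table in Appendix C will be recorded as adverse events". The findings assessed include ulceration, abscess, drainage, scarring and regional lymphadenopathy. No end date is attached to this rule.

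Appendix A has a row headed "Solicited and unsolicited injection site reaction adverse events (incl. concomitant medications", marked at D0, D7, D28 and D56 only. The site-examination row, with a swab if there is discharge, is marked at D0, D7, D28, D56, D182, D365 and early termination.

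In Section 8.3 the D56 list names injection site reactions, both solicited and unsolicited, among the AEs to record. The D182 list reads: "Record any adverse events, including unsolicited adverse events and serious adverse events (including concomitant medications". The D365 list (8.4) and the early-termination list (8.5) likewise leave injection site reactions out of the AE item. All three keep the examination and swab.

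Section 12.4.4.1 defines the primary safety variable as the "frequency of unsolicited, solicited adverse events and injection site reactions at all available post-vaccination time points". It applies a Cochran-Mantel-Haenszel test to injection-site AEs to assess the effect of dose.

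**The concern.** The schedule and the analysis describe different data. Staff or database builders working from Appendix A would close the injection-site-reaction category after D56, for unsolicited as well as solicited events. Those working from Section 10.1 would keep recording qualifying findings to D365. A draining site first seen at D182 could therefore be filed as an injection-site AE or as a general unsolicited AE. If Appendix A is taken at its word, it might stay in the examination record alone.

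What is at stake is the comparison of local reactions by dose. This is a live intradermal vaccine, and Section 3.3.1 says the top dose's safety profile in infants is not yet known. The D182 review by the DSMB (Sections 12.3.1 and 12.3.2) feeds the Phase III dose choice. With 25 infants per dose, how one or two late events are classified can change the picture.

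The recording rule in Section 10.1 has a further weakness: it depends on criteria in Appendix C, and that appendix has none for local reactions.

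**Working it through.** There is no stated figure to reproduce. Section 12.2 says the 99 infants were not chosen on statistical grounds. The check is a comparison of passages.

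| Source | After the D56 visit |
|---|---|
| 10.1, solicited reactions | stop |
| Appendix A, solicited and unsolicited injection-site AEs | not marked at D182, D365 or early termination |
| 8.3 (D182), 8.4, 8.5, AE items | injection site reactions no longer named |
| Appendix A, general unsolicited AEs | marked at D182, D365 and early termination |
| Appendix A, site examination and swab | marked at D182, D365 and early termination |
| 10.1, findings at examination | recorded as AEs, no end date |
| 12.4.4.1, primary safety variable | injection site reactions at every available time point |
| 12.4.4.1, dose test | injection-site AEs; no time window and no solicited/unsolicited rule |

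**Step 1, recording.** The second row conflicts with the sixth and seventh. It cannot be read as merely closing the solicited period, because its label covers unsolicited reactions too.

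**Step 2, grading.** Appendix C contains serum chemistry and haematology only. Tenderness, erythema, induration, ulceration, scar and regional lymphadenopathy are graded in Appendix B. Read literally, no local reaction can meet the criteria that Section 10.1 cites.

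**Step 3, visits affected.** Clinic examinations from D0 to D365 number six (D0, D7, D28, D56, D182, D365). Four have the injection-site AE row marked and two do not, so 2/6. Early termination is a further unmarked examination.

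**Step 4, calendar time.** To D365: 365 − 56 = 309 days, and 309/365 = 84.7%. If the D56 visit falls at D63, the late end of its ±7-day window: 365 − 63 = 302, and 302/365 = 82.7%. To the D182 review: 182 − 56 = 126, and 126/182 = 69.2%. These are shares of days, not of events.

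**Step 5, illustration under assumed rates.** The documents give no rate of late-onset local reactions. If the per-infant probability were p, the chance of at least one in an arm of n is 1 − (1 − p)^n.

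| Assumed p | n = 25 (one dose arm) | n = 24 (BCG) |
|---|---|---|
| 1% | 22.2% | 21.4% |
| 2% | 39.7% | 38.4% |
| 5% | 72.3% | 70.8% |
| 10% | 92.8% | 92.0% |

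One event more or less moves a dose arm's percentage by 1/25 = 4.0 points and the BCG percentage by 1/24 = 4.2 points.

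**The case against.** A reader might infer that late ulcers, draining nodes and scars fall outside the primary reactogenicity measure and are therefore under-counted. The documents do not support that.

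- Section 4.2.1 lists unsolicited AEs among the primary safety and reactogenicity endpoints. They are collected to trial completion, and the general row in Appendix A is marked at D182, D365 and early termination.
- The AE items at D182 and early termination cover any adverse event, with the named types given as inclusions. They are not exclusive lists.
- The dose test in 12.4.4.1 has no D56 limit. Read literally, late reactions are in it.
- Scar is not a solicited term at any time, so the D56 limit removes nothing from the solicited measure on that account.
- Reactions that start by the D56 visit are not lost. Section 10.4 follows them until resolved, otherwise explained, or study completion, and Section 10.2.1 records the highest severity over the whole event.
- D56 is not a sharp boundary. Collection runs to the visit, which may fall from D49 to D63, so an onset at D60 can be inside the solicited period and one at D55 outside it.
- Suppurative lymphadenitis is among the pausing triggers in Section 10.5 with no onset limit, and the D182 review receives all available safety data.
- Section 12.4 defers detail to a statistical analysis plan to be finalised before database lock.

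Most of this stands, and it removes any claim of certain loss. Loss of default relatedness after D56 is not in itself a fault either, since Section 10.2.1 asks the investigator to weigh other causes. What it does not remove is the conflict. The protocol treats injection site reactions as a category of their own (Appendix A, the D56 list, Sections 16.4 and 16.6), and the row that closes at D56 expressly includes unsolicited ones. A later analysis plan can choose how to tabulate, but it cannot restore a classification that was not captured consistently. The appendix citation is a small slip: Section 10.2.4 names all three grading appendices, and only Appendix B has local rows. It nevertheless sits in the one rule that governs late examination findings.

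**Conclusion.** The plan is wrong as written on a narrow point. Appendix A and the D182, D365 and early-termination AE items do not agree with Sections 10.1 and 12.4.4.1 on whether a reaction first appearing after the D56 visit is recorded as an injection-site AE. Section 10.1 also points to a table that cannot grade it. The consequence is inconsistent recording and classification, with possible omission from the dose comparison of injection-site AEs.

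The reach is two of six scheduled clinic examinations plus early termination. The shares of follow-up time (84.7% to D365, 69.2% to D182) show how long the ambiguity lasts. It would be wrong to read them as a proportion of reactions missed, because no late-onset rate is given and Section 10.1 itself describes solicited events as common soon after vaccination. The conclusion rests only on the text of the passages; the probabilities in the working rest on assumed rates.

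**What to change.** 1. In Appendix A, mark injection-site-reaction AEs at D182, D365 and early termination, noting that after the D56 visit these are examination-detected and unsolicited. Name them in the AE items of 8.3 (D182), 8.4 and 8.5.
2. In the site-examination paragraph of 10.1, replace the reference to Appendix C with Appendix B.
3. In 12.4.4.1, state that injection-site AEs with onset after the D56 visit are included in the dose comparison whatever causality is assigned, and are also shown separately from the solicited period.
4. Keep investigator assessment of causality for these later events. Extending default relatedness to D365 is not needed to settle the conflict.

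The cost is a wording change and some extra eCRF fields. The examinations and swabs are already scheduled, so no visit or procedure is added. The small downside is that more low-grade local events, mainly scars, will be tabulated in every arm.

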10.2 Methods and Timing for Assessing, Recording, and Analyzing Safety Parameters

10.2.1 Adverse Events

Definition of an Adverse Event

An adverse event (AE) means any untoward medical occurrence associated with the use of a drug in humans, whether or not considered drug related. An adverse event (also referred to as an adverse experience) can be any unfavorable and unintended sign (e.g., an abnormal laboratory finding), symptom, or disease temporally associated with the use of a drug and does not imply any judgment about causality. An adverse event can arise with any use of the drug (e.g., off-label use, use in combination with another drug) and with any route of administration, formulation, or dose, including an overdose.

Medical conditions that exist prior to administration of the investigational product (pre-existing conditions) will be recorded in the participant's medical history to establish baseline. Day-to-day fluctuations in pre-existing conditions that do not represent a clinically significant change in the participant's status will not necessarily be reported as adverse events.

Any adverse change from the participant's baseline condition (determined from screening evaluations conducted to confirm study eligibility) that occurs following the administration of the investigational product will be considered an adverse event. This includes the occurrence of a new adverse event or the worsening of a baseline condition, whether or not considered related to the investigational product. Intermittent conditions may be present on Study Day 0 but may represent an adverse event if the intensity or duration of the event is worse than usual following receipt of investigational product. Adverse events include but are not limited to: adverse changes (including clinically significant laboratory and vital sign changes) from baseline that represent increases in toxicity grade according to the Toxicity Table (see protocol appendices), adverse changes in the general condition of the participant, signs and symptoms noted by the caregiver of the participant, concomitant disease with onset or increased severity after investigational product administration, and clinically significant abnormalities in laboratory safety parameters occurring after investigational product administration.

The reporting period for all adverse events is specified in Section 10.1. Adverse events will be reported using a recognized medical term or diagnosis that accurately reflects the event. Adverse event evaluations will be reviewed by the principal investigator or sub-investigator. AE information is to be completed by members of the study team designated in writing by the principal investigator. The onset and resolution dates of the event and action taken in response to the event will be documented.

Assessing Severity

The safety concepts of "severity" and "seriousness" are distinct concepts (see Section 10.2.3). "Severity" refers to a degree of clinical manifestation. "Seriousness" refers to defined outcomes from an adverse event. A severe adverse event is not always serious, and a serious adverse event is not always severe.

For all adverse events, the investigator is responsible for assessing the severity of the event and the causal relationship of the event to the investigational product.

The severity of all adverse events, including clinical findings and abnormal laboratory values, will be classified as one of the following grades:

- 1. Mild
- 2. Moderate
- 3. Severe

Toxicity Tables are provided in the protocol appendices for the assessment of severity of specified adverse events. The Toxicity Table Adverse Event Grades do not correlate directly with the classical severity grades of mild, moderate and severe. FOR THE PURPOSES OF RECORDING EVENTS ON THE eCRF, Toxicity Table Grade 1 events will be considered mild in severity, Toxicity Table Grade 2 events will be considered moderate in severity, and both Toxicity Table Grade 3 and 4 events will be considered as severe.

For adverse events not listed in the Toxicity Table determination of severity requires some level of interpretation as outlined below. The degree of incapacity caused by the adverse event and the level of medical intervention required for treatment may be helpful in assessing the overall severity of the adverse event.

For example:

- "Mild" events are generally regarded as noticeable but have no impact on normal activities; they may or may not require over-the-counter treatment managed by the participant's caregiver.
- "Moderate" events generally have some impact on an individual's normal activities and may require general symptomatic medical intervention by a healthcare professional or by the participant's caregiver.
- "Severe" adverse events may be incapacitating, leading to suspension of normal daily activities, and would generally require more immediate medical evaluation and intervention by a healthcare professional.

A change in severity of an adverse event will not be recorded as a new adverse event. Only the highest severity level that occurs during the entire period of the adverse event will be recorded on the eCRF with the onset and resolution dates encompassing the entire duration of the event.

Assessing Causal Relationship (Relatedness)

For all adverse events, the investigator and, for SAEs, the sponsor and local medical monitor, will determine a **causal relationship** to the investigational product without knowledge, for blinded studies, of whether active vaccine or active control was administered. A number of factors will be considered in making this assessment, including: 1) the temporal relationship of the event to the administration of the investigational product 2) whether an alternative etiology has been identified, and 3) biological plausibility.

The investigator will use the following guidelines to assess the causal relationship of an adverse event to study vaccine:

- Not Related to study vaccine (i.e., there is no evidence of a causal relationship; another
 etiology is known to have caused the adverse event. The alternative etiology should be
 documented in the participant's study record).
- **Unlikely Related** to study vaccine (i.e., there is less than a reasonable possibility that the adverse event was caused by study vaccine).
- Possible relationship to study vaccine (i.e., there is a reasonable possibility that the
 adverse event was caused by study vaccine. There must be a plausible mechanism for
 the event to be related to study vaccine. The evidence is inadequate to accept or reject,
 or favours rejection of, a causal relationship; an association exists between the event and
 the study vaccine but there may also be an alternative etiology, such as characteristics of
 the participant's clinical status or underlying condition).
- Probable relationship to study vaccine (i.e., it is likely that the adverse event was caused
 by administration of the study vaccine. The evidence favours acceptance of a causal
 relationship; an association exists between the event and receipt of the study vaccine and
 there is a plausible mechanism for the event to be related to the study vaccine, and an
 alternative etiology is not apparent).
- Definite relationship to study vaccine (i.e., the study vaccine is known to be the cause of
 the adverse event. The evidence establishes a causal relationship; an association exists
 between the event and receipt of the study vaccine and there is a plausible mechanism
 for the event to be related to the study vaccine and causes other than the study vaccine
 have been ruled out).

It is expected that communication and consultation with the sponsor and local medical monitor/research monitor will occur in the assessment of the causality of serious adverse events.

Every effort should be made by the investigator to determine the existence of any pre-existing conditions (e.g., medical conditions on Study Day 0 with onset prior to study vaccination) that

must be taken into consideration when assessing causal relationship of an adverse event. Pre-existing conditions should be recorded in the eCRF as baseline history and substantiated by appropriate source documentation. Intermittent conditions may not be present on Study Day 0 but may represent an adverse event if the intensity or duration of the event is worse than usual following investigational product.

Definition of an Adverse Reaction

An adverse reaction is an adverse event judged to be related to investigational product.

Assessing Expectedness of Adverse Events

Expected adverse events are adverse events consistent with the applicable product information provided by the sponsor (the investigator's brochure for an investigational product). The sponsor, in conjunction with the local medical monitor/research monitor, determines expectedness of related serious adverse events.

